12.5.3 Pharmacokinetics

LOU064 blood concentration data will be listed by treatment, subject, and visit/sampling time point. Descriptive summary statistics for PK concentration will be provided by treatment and visit/sampling time point, including the frequency (n, %) of concentrations below the LLOQ and reported as zero.

Summary statistics will include mean (arithmetic and geometric), standard deviation (SD), coefficient of variation (CV) (arithmetic and geometric), median, minimum and maximum. Concentrations below LLOQ will be treated as zero in summary statistics and for PK parameter calculations.

PK parameters will be listed by treatment and subject. Descriptive summary statistics for PK parameters will be provided by treatment. An exception to this is T_{max} where median, minimum and maximum will be presented.

Table 12-1 Non-compartmental pharmacokinetic parameters

AUC _{last}	The AUC from time zero to the last measurable concentration sampling time (t _{last}) (ng x h/mL)
AUC _{inf}	The AUC from time zero to infinity (ng x h/mL)
AUC _{tau}	The AUC calculated to the end of a dosing interval (tau) at steady-state (ng x h/mL)
C _{max}	The maximum (peak) observed plasma, blood, serum, or other body fluid drug concentration after single dose administration (ng/mL)
T _{max}	The time to reach maximum (peak) plasma, blood, serum, or other body fluid drug concentration after single dose administration (h)
Lambda_z	Smallest (slowest) disposition (hybrid) rate constant (1/h) may also be used for terminal elimination rate constant (1/h)
T _{1/2}	The elimination half-life associated with the terminal slope (λ_z) of a semi logarithmic concentration-time curve (h). Use qualifier for other half-lives
CL/F	The total body clearance of drug from the plasma (L/h)
Vz/F	The apparent volume of distribution during terminal phase (associated with λ_z) (L)

The PK profile of LOU064 will be characterized but not limited to the PK parameters listed above.

12.8 Sample size calculation

Primary endpoint(s)

The primary objective of this study is to characterize the dose-response relationship among LOU064 q.d. and b.i.d doses (10 mg, 35 mg 100 mg q.d and 10 mg, 25 mg and 100 mg b.i.d) and placebo with respect to change from baseline in UAS7 at Week 4. The sample size was determined with the software R, version 3.0.3.

13 Ethical considerations and administrative procedures

13.1 Regulatory and ethical compliance

This clinical study was designed and shall be implemented, executed and reported in accordance with the ICH Harmonized Tripartite Guidelines for Good Clinical Practice, with applicable local regulations (including European Directive 2001/20/EC, US CFR 21), and with the ethical principles laid down in the Declaration of Helsinki.

13.2 Responsibilities of the investigator and IRB/IEC

Before initiating a trial, the investigator/institution must obtain approval/favorable opinion from the IRB/IEC for the trial protocol, written ICF, consent form updates, subject recruitment procedures (eg advertisements) and any other written information to be provided to subjects. Prior to study start, the investigator is required to sign a protocol signature page confirming his/her agreement to conduct the study in accordance with these documents and all of the instructions and procedures found in this protocol and to give access to all relevant data and records to Novartis monitors, auditors, Novartis Quality Assurance representatives, designated agents of Novartis, IRBs/IECs, and regulatory authorities as required. If an inspection of the clinical site is requested by a regulatory authority, the investigator must inform Novartis immediately that this request has been made.

13.3 Publication of study protocol and results

The protocol will be registered in a publicly accessible database such as clinicaltrials.gov and as required in EudraCT. In addition, after study completion (eg defined as last subject last visit) and finalization of the study report the results of this trial will be submitted for publication and posted in a publicly accessible database of clinical trial results, such as the Novartis clinical trial results website and all required Health Authority websites (eg Clinicaltrials.gov, EudraCT etc.).

For details on the Novartis publication policy including authorship criteria, please refer to the Novartis publication policy training materials that were provided to you at the trial investigator meetings.

13.4 Quality control and quality assurance

Novartis maintains a robust Quality Management System (QMS) that includes all activities involved in quality assurance and quality control, to ensure compliance with written Standard Operating Procedures as well as applicable global/local GCP regulations and ICH Guidelines.

Audits of investigator sites, vendors, and Novartis systems are performed by auditors, independent from those involved in conducting, monitoring or performing quality control of the clinical trial. The clinical audit process uses a knowledge/risk based approach.

Audits are conducted to assess GCP compliance with global and local regulatory requirements, protocols and internal Standard Operating Procedures (SOPs), and are performed according to written Novartis processes.

14 Protocol adherence

This protocol defines the study objectives, the study procedures and the data to be collected on study participants. Additional assessments required to ensure safety of subjects should be administered as deemed necessary on a case by case basis. Under no circumstances including incidental collection is an investigator allowed to collect additional data or conduct any additional procedures for any purpose involving any investigational drugs under the protocol, other than the purpose of the study. If despite this interdiction prohibition, data, information, observation would be incidentally collected, the investigator shall immediately disclose it to Novartis and not use it for any purpose other than the study, except for the appropriate monitoring on study participants.

Investigators ascertain they will apply due diligence to avoid protocol deviations. If an investigator feels a protocol deviation would improve the conduct of the study this must be considered a protocol amendment, and unless such an amendment is agreed upon by Novartis and approved by the IRB/IEC and health authorities, where required, it cannot be implemented.

16.1 Appendix 1: Clinically notable laboratory values and vital signs

The following specific criteria have been identified for this study. Should these criteria be met, a re-test must be done within 5 days after the first assessment. Discontinuation of the study treatment should be considered if the abnormal hematology parameter is confirmed:

Hemoglobin: < 10 g/dl

Platelets: < 75 000/mm³

White blood cells: < 3 000/mm³

Neutrophils: < 1 500/mm³

For all other laboratory assessments, the central laboratory will flag laboratory values falling outside of the normal ranges on the central laboratory report (which the investigator should review and sign-off) and the investigator will report any values considered clinically significant in the eCRF.

Notable values for vital signs and change from baseline will be summarized.

Notable values are defined as follows: heart rate of < 60 and > 100 bpm; systolic blood pressure of < 90 and \geq 140 mmHg; diastolic blood pressure of < 60 and \geq 90 mmHg.

For ECGs a notable QTc value is defined as a QTc (Fridericia's) interval of greater than 450 msec for males or greater than 460 msec for females – all such ECGs will be flagged by the central CRO's cardiologist and require assessment for clinical relevance by the investigator.

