- *Impaired platelet function:* BTK is a signaling kinase in one of several platelet activation pathways. In the prescribing information for both ibrutinib and acalabrutinib, bleeding/bruising events are very common and affecting approximately 50% of patients with hematologic malignancies. Warnings on hemorrhagic events including deaths have also been described (see SmPC for ibrutinib and acalabrutinib). Compared to other drugs in the same class, LOU064 demonstrated a higher selectivity for BTK vs. other TEC kinases. Thus, bleeding may be less a safety concern when compared to ibrutinib and acalabrutinib. Patients receiving LOU064 must be closely monitored for any signs and symptoms of bleeding while in the study. Subjects with a known history of bleeding disorder, subjects taking medication that is known to increase the bleeding risk (other than acetylsalicylic acid), and subjects with an increased thromboembolic risk must be excluded from the study (see details in [Section 5.2](#)).
- *Myelomodulation:* The role of BTK inhibition in myelomodulation is not fully understood. Treatment emergent grade 3 or 4 cytopenias (neutropenia, thrombocytopenia and anaemia) were reported in patients with hematologic malignancies treated with ibrutinib and acalabrutinib (see SmPC for ibrutinib and acalabrutinib). Therefore, patients must be closely monitored for signs and symptoms of cytopenia while in the study, and those with a history of hematological disorders or with markedly altered hematologic parameters at baseline must be excluded from the study (see details in [Section 5.2](#)).
- *Risk of cardiovascular origin:* LOU064 is an *in vitro* inhibitor of the hERG channel protein, without affecting other ion channels.

For ibrutinib, atrial fibrillation was described for 3% to 6% of subjects across multiple trials which might be associated with Na-channel inhibition (see SmPC for ibrutinib). For acalabrutinib, both atrial fibrillation and atrial flutter of any grade were reported in 3% of patients (see SmPC for acalabrutinib). Therefore, an intensive ECG monitoring strategy be implemented in this study (see [Section 8.4.2](#)). In addition, patients with a known history or current diagnosis of ECG abnormalities indicating significant risk of safety will be excluded from the study (see details in [Section 5.2](#)).

- *Drug-drug interactions:*

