6.1.3 Treatment arms/group

Subjects will be assigned at Day 1 to one of the following 7 treatment arms (Table 6-2) in a ratio of 1:1:1:1:1:1:1. Each subject will take 2 capsules in the morning and 2 capsules in the evening at home (except for Week 4 and Week 12 morning dose, which are to be taken on site during the site visit), for a total of 4 capsules daily. Depending on the treatment arm, these capsules will contain LOU064 at different dose strengths or placebo. The patient must take one capsule from each morning bottle (identified with a sun symbol) in the morning and one capsule from each evening bottle (identified with a moon symbol) in the evening.

Table 6-2 Treatment regimen per arm

		Number of capsules per intake per treatment arm						
		Arm A: 10 mg LOU064 qd	Arm B: 35 mg LOU064 qd	Arm C: 100 mg LOU064 qd	Arm D: 10 mg LOU064 bid	Arm E: 25 mg LOU064 bid	Arm F: 100 mg LOU064 bid	Arm G: Placebo
Morning dose	10 mg LOU064	1	1	0	1	0	0	0
	25 mg LOU064	0	1	0	0	1	0	0
	50 mg LOU064	0	0	2	0	0	2	0
	Placebo	1	0	0	1	1	0	2
Evening dose	10 mg LOU064	0	0	0	1	0	0	0
	25 mg LOU064	0	0	0	0	1	0	0
	50 mg LOU064	0	0	0	0	0	2	0
	Placebo	2	2	2	1	1	0	2

Treatment duration

All subjects will receive their respective LOU064 or placebo capsules for 12 weeks (from Day 1 until Week 12).

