8.4.1 Laboratory evaluations

A central laboratory will be used for analysis of all specimens detailed in this section ([Table 8-9](#)) unless noted otherwise. Details on the collections, shipment of samples and reporting of results by the central laboratory are provided to investigators in the laboratory manual.

Clinically notable laboratory findings are defined in [Appendix 1](#).

Clinically significant abnormalities must be recorded on the relevant section of the eCRFs capturing medical history/current medical conditions/AEs.

Table 8-9 Laboratory assessments

Test Category	Test Name
Hematology	Hematocrit, Hemoglobin [only in case of clinically significant anemia, the following parameters will be assessed: Mean Corpuscular Hemoglobin (MCH), Mean Corpuscular Hemoglobin Concentration (MCHC), Mean Corpuscular Volume (MCV)], Platelets, Red blood cells (RBC), White blood cells (WBC) and Differential (Basophils, Eosinophils, Lymphocytes, Monocytes, Neutrophils, Bands)
Chemistry	Albumin, Alkaline phosphatase (ALP), ALT, AST, Gamma-glutamyl-transferase (GGT), Lactate dehydrogenase (LDH), Calcium, Magnesium, Phosphorus, Chloride, Sodium, Potassium, Creatinine Kinase (CK), Creatinine, total Bilirubin (in case of clinically significant elevation: direct Bilirubin and indirect Bilirubin will be assessed)
	Only at baseline (Day 1) and Week 12: total Cholesterol, Low density Lipoprotein (LDL), High density Lipoprotein (HDL), Total Protein, Triglycerides, Blood Urea Nitrogen (BUN) or Urea, Uric Acid, Amylase, Lipase, Glucose (fasting)
	Only at screening and baseline and when deemed necessary by the investigator: C-reactive Protein (CRP)
Urinalysis	Done on site: Macroscopic Panel (Dipstick) (Color, Bilirubin, Blood, Glucose, Ketones, Leukocytes esterase, Nitrite, pH, Protein, Specific Gravity, Urobilinogen)
Coagulation	Prothrombin time (PT)/International normalized ratio (INR), Partial thromboplastin time (PTT), Activated partial thromboplastin time (APTT)

Test Category	Test Name
Hepatitis markers	At Screening only: Hepatitis B surface antigen (HBsAg), anti-HBsAg antibodies (HBsAb), antibodies against Hepatitis B core antigen (HBcAb) and Hepatitis B-Deoxyribonucleic acid (HBV- DNA) as appropriate; Hepatitis C virus antibodies (HCVAb) and Hepatitis C-Ribonucleic acid (HCV-RNA) as appropriate
Additional tests	IgE, [REDACTED]; Follicle-stimulating hormone (FSH) (for female subjects with unclear fertility status), serum pregnancy test (for WoCBP)

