9.1 Discontinuation

9.1.1 Discontinuation of study treatment

Discontinuation of study treatment for a subject occurs when study treatment is stopped earlier than the protocol planned duration, and can be initiated by either the subject or the investigator.

Patients may voluntarily discontinue investigational treatment for any reason at any time.

The investigator must discontinue study treatment for a given subject if, he/she believes that continuation would negatively impact the subject's well-being.

Study treatment must be discontinued under the following circumstances:

- Subject/guardian decision
- Pregnancy
- Use of prohibited treatment as per recommendations in the prohibited treatment section
- Any situation in which study participation might result in a safety risk to the subject, eg required surgical interventions associated with a risk for clinically significant bleeding
- Following emergency unblinding
- Emergence of the following AEs:
 - AEs including hypersensitivity reactions, severe/serious infections (i.e., requiring specific intravenous/intramuscular anti-infectious therapy and/or hospitalization), thromboembolism, clinically significant spontaneous bleeding events and clinically significant ECG abnormalities (eg QT prolongation) for which continued exposure to the study drug would be detrimental
 - Abnormal liver laboratory results requiring discontinuation (see [Appendix 2](#))
 - Abnormal renal laboratory results requiring discontinuation (see [Appendix 3](#))
 - Platelets < 75 000/mm³

- Any other laboratory abnormalities that in the judgment of the investigator, taking into consideration the subject's overall status, prevents the subject from continuing participation in the study
- Patient received a live virus vaccination during the study

If discontinuation of study treatment occurs, the investigator should make a reasonable effort to understand the primary reason for the subject's premature discontinuation of study treatment and record this information.

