6. its outcome i.e., its recovery status or whether it was fatal

Conditions that were already present at the time of informed consent should be recorded in medical history of the subject.

AEs (including lab abnormalities that constitute AEs) should be described using a diagnosis whenever possible, rather than individual underlying signs and symptoms.

AE monitoring should be continued for at least 30 days following the last dose of study treatment.

Once an AE is detected, it must be followed until its resolution or until it is judged to be permanent (eg continuing at the end of the study), and assessment must be made at each visit (or more frequently, if necessary) of any changes in severity, the suspected relationship to the study drug, the interventions required to treat it, and the outcome.

Information about adverse drug reactions for the investigational drug can be found in the IB.

Abnormal laboratory values or test results constitute AEs only if they fulfill at least one of the following criteria:

- they induce clinical signs or symptoms
- they are considered clinically significant
- they require therapy

Clinically significant abnormal laboratory values or test results must be identified through a review of values outside of normal ranges/clinically notable ranges, significant changes from baseline or the previous visit, or values which are considered to be non-typical in subjects with the underlying disease. See [Appendix 1](#), [Appendix 2](#) and [Appendix 3](#) for alert ranges for laboratory and other test abnormalities.

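### Platelets below 75 000/mm³ are a mandatory stop in Protocol 9.1.1, but Appendix 1 at the same count asks for a re-test and then only for stopping to be considered

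*Protocol*

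**What the plan says.** Protocol 9.1.1 opens its list of stopping rules with "Study treatment must be discontinued under the following circumstances". One entry, placed under the sub-heading on emerging adverse events, reads "Platelets < 75 000/mm³". It carries no re-test or confirmation condition.

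Protocol 16.1 (Appendix 1) gives criteria for four hematology parameters: hemoglobin, platelets, white blood cells and neutrophils. The platelet limit is the same, below 75 000/mm³. For all four the instruction is "Should these criteria be met, a re-test must be done within 5 days after the first assessment", followed by "Discontinuation of the study treatment should be considered if the abnormal hematology parameter is confirmed".

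Two other sections direct the reader to Appendix 1. In 8.4.1 the text is "Clinically notable laboratory findings are defined in" Appendix 1. In 10.1.1 Appendices 1, 2 and 3 are cited "for alert ranges for laboratory and other test abnormalities".

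**The concern.** The same laboratory result leads to two different instructions. A site that looks up a low platelet count in Appendix 1 finds what appears to be a complete procedure: repeat the test, confirm the value, consider stopping. Nothing there tells the site that 9.1.1 has already made the decision.

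At stake is whether a stopping rule for a risk that the protocol itself names is applied in the same way at every site. Section 4.6 lists impaired platelet function and myelomodulation among the potential risks to be monitored closely. For two approved drugs of the class, in patients with hematologic malignancies, it notes: "Treatment emergent grade 3 or 4 cytopenias (neutropenia, thrombocytopenia and anaemia) were reported". Section 5.2 excludes subjects with platelets below 100 000/mm³ at screening, so a count below 75 000/mm³ on treatment would normally be a real fall and not a continuation of the entry value.

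**Working it through.** The plan states no figure to reproduce. The check is a comparison of texts, followed by a bound on the extra dosing.

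**1. The two rules side by side**

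| | Protocol 9.1.1 | Protocol Appendix 1 |
|---|---|---|
| Platelet limit | below 75 000/mm³ | below 75 000/mm³ |
| Confirmation needed | none stated | re-test within 5 days |
| Action | treatment must stop | stopping to be considered if confirmed |
| Pointer to the other text | none | none |

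The limits agree. The actions differ in trigger (the count itself against a confirmed count) and in force (mandatory against discretionary). Removing the first difference would not remove the second: a confirmed count below the limit is still a mandatory stop in one place and a matter for consideration in the other.

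**2. Search for text that reconciles them**

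- The liver and renal items in 9.1.1 refer to Appendices 2 and 3. The platelet item has no reference to Appendix 1.
- The platelet item sits under an adverse-event sub-heading, and 10.1.1 counts a laboratory value as an adverse event only if it causes signs or symptoms, is clinically significant or needs therapy. On that reading an asymptomatic low count might fall outside the rule. But 9.1.1 names the bare count as the stopping event, and its next entry leaves *other* laboratory abnormalities to the investigator's judgment. The platelet item is therefore not a judgment item.
- No section of the protocol or SAP says which text takes precedence.

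**3. How many parameters conflict**

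Appendix 1 lists 4 hematology criteria. Section 9.1.1 names 1 of them, platelets. The conflict covers 1 of 4. The other three have no mandatory counterpart in 9.1.1.

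**4. Extra dosing**

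Let *L* be the days from the first blood draw to the known result, and *t* the days from that draw to the re-test draw, with *t* at most 5. Under 9.1.1 dosing continues until day *L*, since nobody can act on an unknown result. Under Appendix 1 alone it can continue at least to day *t*. The excess before the re-test draw is

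*t* − *L*, at most 5 − *L* days.

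The documents do not give *L*. Over an assumed range:

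| *L* (days, assumed) | Largest excess before re-test draw (days) |
|---|---|
| 0 | 5 − 0 = 5 |
| 1 | 5 − 1 = 4 |
| 2 | 5 − 2 = 3 |
| 3 | 5 − 3 = 2 |

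The wait for the re-test result is not included. After a confirmed low count, Appendix 1 sets no limit on further dosing.

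**5. When it can matter**

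Protocol Table 8-10 describes the Week 12 sampling day as the last day and last dose, and Week 16 is follow-up. A low count at either visit leads to no further dosing under either text. The scheduled post-baseline visits before the last dose are Weeks 2, 4 and 8; unscheduled draws in the treatment period add to these.

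**The case against.** The best defense is that the texts can be read together. Appendix 1 has one general sentence for four parameters, while 9.1.1 has a specific rule for platelets and is the section on discontinuation. The specific, stricter rule should govern, and a site that stops treatment and also re-tests complies with both. Sections 8.4.1 and 10.1.1 send sites to Appendix 1 to identify notable values and alert ranges, not to decide on stopping; where the liver section (10.2.1) cross-refers on stopping, it names the discontinuation section. Section 9.1.1 also requires a stop whenever the investigator believes that continuing would harm the subject, and 14.1 expects immediate action for safety.

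Most of this stands, and it limits the hazard. It does not remove the inconsistency. Although Appendix 1 is reached as a list of notable values, it goes on to give a stopping instruction, and that instruction is weaker than the mandatory one.

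The documents also do not show whether the sponsor wanted a stop on a single value or on a confirmed one. That is a fair point about the remedy, and the fix allows for it.

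A reader might infer that the whole 5-day window, with ten morning and evening intakes, is extra exposure. It is not: dosing also continues under 9.1.1 until the first result is known. A reader might also add the ban on interruptions in 6.5 as a second conflict. The liver and renal provisions can reasonably be read as exceptions to it, and the action list in 10.1.1 and the tabulation in SAP 2.7.1 are recording and reporting text that permit nothing.

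**Conclusion.** The inconsistency is real and should be corrected. It is confined to platelets. Its size is at most 5 days minus laboratory turnaround before the re-test, with no stated limit in Appendix 1 after confirmation. It takes effect only if a site acts on Appendix 1 without consulting 9.1.1, and only for counts taken before the last dose.

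A reader might infer damage to the primary analysis or to safety oversight. The documents do not support either. SAP 2.5.3 uses all available data under a treatment policy approach, so a subject's data are used whether or not treatment stops. The trigger for the internal safety board in Protocol 10.2.3 refers to 9.1.1, not Appendix 1. No event rate is given for counts below 75 000/mm³, so the number of subjects affected cannot be estimated.

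**What to change.** In Appendix 1, keep the re-test within 5 days for all four parameters. For platelets only, replace the discretionary wording with: *study treatment must be discontinued (see 9.1.1); the re-test is follow-up*. Add a pointer to Appendix 1 at the platelet item in 9.1.1. Leave hemoglobin, white cells and neutrophils unchanged.

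If the sponsor intended a stop only on a confirmed value, state the confirmation step in both places and keep the stop mandatory once the value is confirmed.

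The cost is a wording amendment, with the sponsor, ethics committee and, where required, health authority approvals set out in 14.1, and a notice to the approximately 90 planned centers. It needs no extra data, visits or subjects.
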